The CDS, the largest prospective study examining the effect of donor age on graft success and cell loss following penetrating keratoplasty for endothelial dysfunction conditions, did track the presence of diabetes in both the donor and recipient with limited historical information, and did not find an effect on either graft success or cell loss compared to donors without diabetes.³ One major limitation of this study was that the presence of diabetes in donors was defined simply by presence or absence of diabetes. Vislisel et al for Descemet stripping endothelial keratoplasty (DSAEK) donors³³ and Price et al for Descemet membrane endothelial keratoplasty (DMEK) donors³⁴ found a similar lack of donor diabetes effect on graft failure, while both series had similar limitations on donor diabetes determination by historical grounds only. However, our group now has suggestive data on the negative impact of donor diabetes on endothelial keratoplasty (EK) outcomes from a secondary analysis of a large prospective multi-center clinical trial, the CPTS. In the CPTS, corneal tissue from donors with diabetes had a significantly greater risk of primary or early graft failure,³⁵ greater long term endothelial cell loss (ECL),³⁶ and increased risk of graft dislocation³⁷ following EK compared to corneas from donors without diabetes.

Since about 1/3 of the nationwide donor pool now includes tissue from donors with diabetes, and there are now conflicting results among studies that were not designed to assess the question of diabetic donor status directly, our group is interested in determining whether corneal tissue from donors without diabetes is indeed superior for EK outcomes, and if severity of donor diabetes correlates with graft success using novel biomarkers of glycemic burden. Finally, the most recent Online Adverse Reaction Reporting System (OARRS) data from the EBAA reported at the Medical Advisory Board meeting in November 2020 showed an unexplained increasing rate of primary and early failures associated with DMEK. The EBAA will be looking at increasing use of pre-loaded lenticules as one source of the issue, but admittedly there is an underreporting issue from surgeons and thus there is no comprehensive database of all the factors that could be contributing to this increasing rate of DMEK primary and early failures.

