5.2 Graft Failure Assessment

Graft failure will be assessed and defined as the occurrence of one of the following:

- Cornea which requires regrafting for any reason
- Cornea which remains cloudy without clearing, according to the following:
 - (1) cloudy cornea which does not clear in the first postoperative week and stays cloudy through 8 weeks post-operatively
 - (2) cloudy cornea which was initially clear in the first postoperative week but becomes and remains cloudy for 3 months without clearing.

OR

- ◆ A study participant whose cornea becomes cloudy (clouded recipient central stroma, based on the DEKS grading scale) will be treated by the investigator's usual routine.

For eyes meeting the definition of graft failure above, the principal cause of graft failure will be classified as one of the following:

- Early failure (cloudy cornea in the first postoperative week which does not clear or requires a regraft within 8 weeks), associated with surgical complications
- Primary donor failure (cloudy cornea in the first postoperative week which does not clear or requires a regraft within 8 weeks), in the absence of surgical complications
- Graft rejection (defined as a clouded recipient central stroma following an allograft reaction);
- Non-rejection graft failure (defined as a graft that initially had a clear central recipient stroma and becomes cloudy due to causes other than an immune event. These include: surface failure, infection, glaucoma/hypotony, endothelial decompensation, interface irregularity or opacity, pre-existing stromal scarring, blunt or penetrating trauma, and other causes);
- Refractive/visual graft failure (defined as a graft that requires regrafting due to inadequate vision while the recipient central stroma remains clear).

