8.2 Statistical Hypotheses

The primary outcome for this study is graft failure by 12 months. The null/alternative hypotheses are:

- Null Hypothesis:* There is no difference in the probability of graft failure by 12 months between the diabetic group and the non-diabetic group.
- Alternative Hypothesis:* The probability of graft failure by 12 months is different for the diabetic and non-diabetic groups.

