- A participant can enroll both eyes into the study, if both are eligible. It is anticipated that about 30% of participants will have two study eyes, based on the CPTS data⁵⁴, data from single site study of Price et al for DMEK⁵⁵, and a participating surgeon survey, indicating more common bilateral cases associated with DMEK, the endothelial keratoplasty procedure in the DEKS, compared to DSAEK which was the procedure in the CPTS. This would mean it is expected that approximately **1092 participants would need to be enrolled in order to enroll 1420 study eyes**.

Although both eyes of a study participant can be enrolled, and/or both eyes of the donor may be provided for the study, the sample size calculation does not adjust for these correlations, for the reasons noted below.

- If participants with two study eyes receive a cornea from a donor with known diabetes for the first eye, the second eye will receive a cornea from a donor without known diabetes. If the first study eye received a cornea from a donor without known diabetes, then there is a 1/3 chance that the second study eye will receive a cornea from a donor with known diabetes. Note, the primary analyses will adjust for these correlations. Those classified as having *known diabetes* are participants with a diabetes diagnosis prior to tissue donation or reclassified as diabetic based on post-mortem HbA1c values.

Regarding donors, CPTS found there were no cases of graft failures occurring from the cornea mates of the same donor because of the low graft failure rate and low number of cornea mates in the study;³⁵ a similar trend is expected in the DEKS and sample size will not be adjusted for this. If there are cases of graft failures occurring from cornea mates both assigned in the study, sensitivity analysis will account for the correlation in the models.

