8.6 Analysis of the Primary Efficacy Endpoint

Summary statistics (Kaplan-Meier estimates of 1-year graft failure with 95% confidence intervals) will be reported by donor diabetes status groups (with versus without diabetes). Further, point estimates and 95% confidence intervals for donor diabetes status group differences will be presented.

One-year graft failure between donor diabetes status groups will be compared using a proportional hazards model while adjusting for corneal diagnosis and accounting for participants who have two study eyes included in the study using a frailty model. The proportional hazards assumption will be tested. If this assumption is violated, then hazard ratios will be presented separately over time. There will be no imputation of missing data in the primary analysis.

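### If the proportional hazards check fails, does Section 8.6 leave the primary test undecided?

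*Combined protocol and SAP*

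**What the plan says.** Section 8.2 states the null hypothesis on the 12-month probability: "There is no difference in the probability of graft failure by 12 months between the diabetic group and the non-diabetic group". Section 8.6 names one comparison: "One-year graft failure between donor diabetes status groups will be compared using a proportional hazards model while adjusting for corneal diagnosis", with a frailty term for participants who contribute two eyes. On the model assumption it says: "The proportional hazards assumption will be tested", followed by: "If this assumption is violated, then hazard ratios will be presented separately over time". It gives neither the form and level of the check nor the periods.

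The same section reports one-year Kaplan-Meier failure estimates by donor group and adds: "Further, point estimates and 95% confidence intervals for donor diabetes status group differences will be presented". That output does not depend on the check. On two-eye participants, Section 8.3 says: "Note, the primary analyses will adjust for these correlations".

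Section 8.1 describes Chapter 8 as a summary, and Sections 8.4.1, 8.5, 8.12, 8.14 and 8.15.2 send detail to a SAP. Section 8.6 does not do so for this point, and the document under review holds no separate SAP text.

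**The concern.** Period hazard ratios and 12-month probability are different targets. One group can have more early and fewer late failures than the other while the 12-month risks are equal. If the check fails, three results are on the table (the overall Cox comparison, the one-year difference, the period ratios), and the text does not rank them. Section 8.13 makes no multiplicity adjustment for the primary analysis. If the period ratios were read as the answer, a difference in timing alone could be reported as a difference in one-year failure.

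A failed check is not far-fetched. Section 1.1 reports from the CPTS that "corneal tissue from donors with diabetes had a significantly greater risk of primary or early graft failure", and Section 5.2 sets early failure apart: "cloudy cornea in the first postoperative week which does not clear or requires a regraft within 8 weeks". Section 1.1 calls those data suggestive and they come from DSAEK, so an early concentration of the excess is plausible rather than expected.

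**Working it through.** **The plan's own figure.** Inputs from Section 8.3: two-sided 5%, 90% power, 2:1 allocation, 5-point difference d. The pooled two-proportion formula for the smaller (diabetic-donor) group is

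n_D = [1.960·√(1.5·p̄(1−p̄)) + 1.2816·√(p_D(1−p_D) + p_N(1−p_N)/2)]² / d².

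- 5% against 10%: p̄ = (0.10 + 2×0.05)/3 = 0.0667; n_D = (0.5988 + 0.4322)²/0.0025 = 425.2, so 426; total 3×426 = 1278.
- 4% against 9%, the rates Section 8.3 lists: p̄ = 0.0567; n_D = (0.5550 + 0.4075)²/0.0025 = 370.6, so 371; total 1113, which is also the table's entry.

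So 1278 comes from the table's 5% column. That makes the trial larger than its listed rates need and has no bearing on this point. The steps below use 852 and 426 eyes.

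**If hazards are proportional.** S_D(t) = S_N(t)^HR, so HR = 1 exactly when the 12-month risks are equal. The Cox comparison then tests the Section 8.2 hypothesis.

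**If they are not.** Strictly the equivalence is lost, but the error is small when few eyes fail. Take an extreme pattern with 6% risk in both groups, split at 8 weeks: non-diabetic 2% + 4%, diabetic 4% + 2%.

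- Expected failures: diabetic 426×0.06 = 25.56; non-diabetic 852×0.06 = 51.12; total 76.68.
- Diabetic share of eyes at risk: 1/3 at the start; 408.96/1243.92 = 0.3288 at 8 weeks; 400.44/1201.32 = 1/3 at 12 months. The average is about 0.3311.
- Log-rank expectation for the diabetic group: 76.68×0.3311 = 25.39, a drift of 25.56 − 25.39 = 0.17 failures.
- Standard deviation: √(76.68×0.3311×0.6689) = 4.12. The drift is 0.17/4.12 = 0.04 standard deviations.

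A shift of that size leaves a two-sided 5% test at essentially 5%.

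**Simulation.** Assumptions: independent eyes, no covariate, failure times uniform within 0 to 8 weeks and 8 weeks to 12 months, check = Wald test of group × log time at 5%. The full-null rows used 15,000 trials and the equal-6% rows 4,000. The last column takes the period ratios as the test whenever the check rejects, and Cox otherwise.

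| Non-diabetic vs diabetic (early + late) | Cox | One-year difference | Period ratios as test |
|---|---|---|---|
| 2%+2% in both | 4.5% | 4.9% | 6.2% |
| 2%+4% in both | 4.7% | 5.1% | 6.4% |
| 2%+4% vs 3%+3% | 4.8% | 5.1% | 19.5% |
| 2%+4% vs 4%+2% | 4.7% | 4.9% | 59.0% |
| 2%+4% vs 4%+2%, 10% censored | 5.9% | 5.9% | 58.9% |

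A second, separately written program gave 18.3% and 59.0% for the last column in the two uncensored timing-shift rows, with Cox at 4.8% and 4.4%. The 5.9% in the censored row is the same for Cox and the difference, so it favours neither. Under the full null, the rule in the last column adds 1.2 to 1.4 points to 5%. If the split could also be picked from four candidates, it reaches 7.3% to 7.6%.

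**Do the timing-shift rows describe this trial?** Both need diabetic-donor grafts to fail less often after 8 weeks: 3/97 = 3.1% against 4/98 = 4.1% in the mild pattern, and 2/96 = 2.1% against 4.1% in the extreme one. Section 1.1 points the other way (more early failure and greater long-term cell loss), and Section 8.3 assumes 9% against 4% overall.

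**Does the choice between Cox and the difference matter?** A simulation used the log-rank test in place of Cox and the unadjusted Kaplan-Meier difference, with 4,000 trials per case and 0% or 10% censoring. A rejected check together with disagreement between the two tests occurred in 0.05% to 0.2% of trials under the full null, 0.5% under the mild shift, and at most 3.0% when the whole 5-point excess was early.

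**Paired eyes and the one-year difference.** Under Section 8.3, a two-eye participant has one eye in each group with probability 1/3 + (2/3)(1/3) = 5/9, two non-diabetic corneas with probability 4/9, and never two from donors with known diabetes. With positive correlation between a participant's eyes and equal risks, split pairs reduce the variance of the difference in proportion to (5/9)/(n_D·n_N). Same-group pairs raise it in proportion to (4/9)/n_N². The net effect is a reduction whenever 5·n_N > 4·n_D, which holds here. An interval that ignored the pairing would be somewhat too wide, not too narrow. Reclassification on post-mortem HbA1c would move a few pairs.

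**The case for a change.** The best case for a change is that the text is silent where it should speak. It replaces one hazard ratio with several exactly when the model is in doubt. Section 8.7 names the estimate, interval and p-value for the secondary endpoint, while Section 8.6 does not say what decides if the check fails. The check could well reject: for 4% against 9%, with 25% to 75% of non-diabetic failures early, it rejected in 16% to 84% of simulated trials if all the excess was early, 5% to 49% if three quarters was, and 4% to 17% if half was. A rule would take two or three sentences.

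What stands is that Section 8.6 does not call the period ratios descriptive, and that the cut-points and the level of the check are open. These are details that analysts settle in a SAP. It does not follow that the test is undecided: one model is named as the comparison, and no section lets a period ratio decide anything. A rejected check is also least troublesome where it is most likely. With all the excess early, a second run gave Cox 94.2% to 94.5% power, and a test of 12-month risk had 93.8% when the excess was confined to the first 8 weeks.

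The natural remedy, switching to a clustered and diagnosis-adjusted one-year difference when the check rejects, is not clearly better. It chooses the test by a pre-test. Its simulated power for a 5-point excess was 91% to 94%, against 93% to 95% for Cox alone. Those figures come from independent eyes without covariates, not from the clustered, adjusted method itself.

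**Conclusion.** No change is needed. Read plainly, the Cox frailty comparison is the primary test whatever the check shows, the one-year Kaplan-Meier difference with its interval is reported beside it, and the period ratios describe timing. On that reading the error rate is 4.7% to 4.8% under both equal-risk timing shifts without censoring, and 5.9% for Cox and the difference alike in the extreme pattern with 10% censoring. The 20% and 59% figures belong to a procedure the plan does not prescribe.

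This rests on assumed failure timings, independent eyes and no covariate in the simulations, and on failure rates of the order Section 8.3 assumes; at much higher rates the Cox comparison and 12-month risk could separate further. A sentence in Section 8.6 or the SAP saying that period ratios are descriptive and that the conclusion rests on the planned Cox comparison, read alongside the one-year difference, would be a courtesy to readers. The analysis is sound without it.

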8.7 Analysis of the Secondary Endpoint

For ECD, only participants with a gradable 1-year image who have not experienced graft failure 1-year after DMEK will be included in the analysis. There will be no imputation of missing data. Summary statistics (mean \pm SD or median (IQR)) appropriate to the distribution will be tabulated by donor diabetes status group and at baseline, 1-year and for the changes from baseline to 1-year.

Repeated measures regression models with unstructured covariance including data from baseline, 1 month, and 1 year will be used to compare donor diabetes status effects while adjusting for baseline ECD, corneal diagnosis, and recipient study eyes (random effect. A point estimate, 95% confidence interval, and two-sided p-value will be reported for the donor diabetes status effect based on the linear regression model. Residual values will be examined for an approximate normal distribution. If residual values from the regression model have a skewed distribution then an appropriate transformation, truncation, or a nonparametric analysis based on ranks will be performed. Descriptive analyses (e.g., boxplots) stratified by donor diabetes status group will be given at baseline, 1 month, and 1 year.

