4.4 Early Termination Visit

Participants will be asked to come for an end of study visit in the event of withdrawal or early termination for another reason. If graft failure occurs in the absence of re-graft, follow-up is not terminated prematurely. However, if the graft is replaced, follow-up will be discontinued.

Chapter 5: Clinical Procedures

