5.5 Specular Microscopy

At the 1 month and 12 month visits, specular microscopy of the central endothelium will be obtained on all participants that have not experienced graft failure.^{5,50,51} Detailed procedures for obtaining best image quality and image transmission will be provided in the DEKS-CIARC Clinical Site Imaging Manual.

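### The ECD analysis drops usable 1-month values and compares surviving grafts only, which may attenuate the donor effect; a failure-inclusive check should be prespecified

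*Combined protocol and SAP*

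**What the plan says.** Section 8.7 sets the analysis population for the secondary endpoint: "only participants with a gradable 1-year image who have not experienced graft failure 1-year after DMEK will be included in the analysis". It adds: "There will be no imputation of missing data". The model follows: "Repeated measures regression models with unstructured covariance including data from baseline, 1 month, and 1 year will be used", adjusted for baseline ECD and corneal diagnosis, with a random effect for the recipient.

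Two other sections determine what data exist. Under section 5.5, at 1 and 12 months, "specular microscopy of the central endothelium will be obtained on all participants that have not experienced graft failure". Under section 4.4, "if the graft is replaced, follow-up will be discontinued". So no 1-year ECD of a failed graft is planned.

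Section 5.2 defines failure broadly. It includes "Cornea which requires regrafting for any reason", and one listed cause is a graft that "requires regrafting due to inadequate vision while the recipient central stroma remains clear". Section 8.5 leaves sensitivity analyses for the secondary outcome to the SAP. Its two examples are adjustment for operative complications and for recipient diabetes.

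**The concern.** The restriction does two separate things.

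- **It removes non-failed eyes that have a 1-month value but no usable 1-year image.** A likelihood-based repeated-measures model can use such eyes directly, so the no-imputation rule is no reason to drop them. With them in the model, missingness at 1 year may depend on the observed 1-month density. Without them, it may depend only on the covariates in the model.
- **It compares survivors only.** Failure is the primary outcome and is designed to differ by donor group. Section 1.1 also hypothesises that donors with more severe or poorly controlled diabetes carry a higher risk of both failure and cell loss. If so, removing failed grafts may take out relatively more low-density eyes from the diabetic-donor group.

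Cell loss is the second stated objective and the key secondary outcome, so a distorted or unclear estimand matters for the trial's message.

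**Working it through.** **Inputs from section 8.3.** Failure 4% (donors without diabetes) and 9% (with diabetes); 2:1 allocation; 1420 eyes, of which 1278 are followed. The last pair agrees with 10% loss: 1278 / 0.90 = 1420. The plan gives no SD, effect size or power for ECD, so there is no ECD figure to reproduce.

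**Assumptions not in the documents.** Normal ECD; ρ, the correlation of 1-year density with the tendency to fail; r, the correlation of 1-month with 1-year density; SD of 300 to 600 cells/mm².

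**1. Eyes left out**

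- Lost: 1420 − 1278 = 142.
- Failed: 852 × 0.04 ≈ 34 and 426 × 0.09 ≈ 38.
- Remaining before ungradable images: about 818 and 388, or 1206 in total.
- Share excluded: 1 − 0.90 × 0.96 = 13.6% against 1 − 0.90 × 0.91 = 18.1%.

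**2. Precision lost through the image rule.** Suppose 10% of non-failed eyes lack a 1-year value but all have a 1-month value. Using them multiplies the variance by about 1 − 0.1r². At r = 0.6 this is 0.964 (SE 1.8% smaller), and at r = 0.8 it is 0.936 (SE 3.3% smaller). Ungradable images would add to this; their share is not given. In a simulation where loss depended on 1-month density, the bias of the restricted analysis was only about 0.002 SD.

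**3. Shift from removing failures.** Among survivors the mean rises by ρ·φ(z_p)/(1 − p) SD:

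- p = 0.04: φ(1.751)/0.96 = 0.0898ρ
- p = 0.09: φ(1.341)/0.91 = 0.1785ρ

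With the same ρ in both groups, the contrast moves toward zero by 0.0887ρ:

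| ρ | Shift (SD) | cells/mm² at SD 300 to 600 |
|---|---|---|
| 0 | 0 | 0 |
| 0.25 | 0.022 | 7 to 13 |
| 0.5 | 0.044 | 13 to 27 |
| 1 | 0.089 | 27 to 53 |

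**4. Direction.** With different links the shift is 0.1785ρ_D − 0.0898ρ_N. It changes sign when ρ_D is below about half of ρ_N (0.0898 / 0.1785 = 0.50). With ρ_N = 0.5 and ρ_D = 0 it is 0.045 SD away from zero. Conversely, a link stronger in the diabetic-donor group would exceed the table values. Equal failure rates with equal links give no shift.

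**5. Can 1-month data repair the failure selection?** Only partly. The simulation also kept the 1-month values of eyes that later failed. At ρ = 1 the 0.089 SD bias became 0.037 (no failure before the 1-month image, r = 0.8), 0.062 (same, r = 0.6), 0.074 (half of failures before it, r = 0.6) or 0.088 (all before it).

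**6. Consistency check on the worst case.** Let a graft fail when density falls below one threshold common to both groups.

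- Failure of 9% against 4% then implies a true difference of 1.751 − 1.341 = 0.41 SD. Survivors show 0.41 − 0.089 = 0.32 SD, an attenuation of about 22%. With 818 and 388 eyes, SE = √(1/818 + 1/388) = 0.062 SD, so power exceeds 99%.
- A true difference of 0.20 SD implies failure of about 6.0% against 4%. The shift is 0.038 SD and survivors show 0.162 SD.
- The same 0.20 SD with ρ = 0.5, and the donor effect acting only through density, gives a shift of 0.009 SD.

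These SE and power figures ignore clustering and covariate adjustment.

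**The case against.** The strongest defence is that ECD in surviving grafts is a legitimate quantity. A failed graft has no planned 1-year ECD, failure is analysed in its own right as the primary endpoint, and a worst-rank composite would partly count that endpoint again. This stands, and it is why the surviving-graft comparison should remain the main analysis.

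Second, the direction of bias is not established. Failure includes regrafting for any reason and visual failure with a clear stroma. Section 1.1 also reports more graft dislocation with diabetic donors in the cited preservation-time trial. Some failures may therefore have little to do with density, and not equally by group. This stands in full.

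Third, a completer analysis does not require images to be missing completely at random, because the model adjusts for baseline ECD and corneal diagnosis. This also stands: the assumption is stronger than needed, but not that strong.

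Fourth, section 8.5 promises sensitivity analyses in the SAP, and its examples are not exhaustive. This stands in part. A fuller SAP may contain a suitable check, but the restriction in 8.7 is a stated rule rather than missing detail, and neither example touches failed grafts or missing images.

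A reader might set the 0.089 SD worst case against the 0.20 SD difference detectable with 90% power ((1.960 + 1.282) × 0.062) and infer that 44% of the effect is lost and power falls to 44%. The documents do not support this. If failures are exactly the lowest-density eyes under a common threshold, the design failure rates imply a 0.41 SD difference, which would still be found. Combining 0.089 with 0.20 needs different density thresholds by donor group, and nothing in the plan suggests them.

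**Conclusion.** The point holds as a modest correction to a key secondary analysis. The image rule excludes data that the chosen model could use. The cost is a small loss of precision (an SE of order 2% to 3% at 10% missing) and an avoidable assumption, with little sign of bias from loss to follow-up alone.

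The survivors-only contrast may attenuate the donor effect. At the design failure rates, and with an equally strong link in both groups, the attenuation is at most about 0.09 SD and about 0.04 SD at a correlation of 0.5. It is zero if failure is unrelated to density, and it may be opposite in sign if the link differs by group. A reader might infer that the rule necessarily biases toward zero; the broad failure definition does not support that. Normality, the SD and the correlations are all assumptions. The unknown direction is itself a reason to prespecify one check that includes the failures.

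**What to change.** In section 8.7, and in the SAP:

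1. Replace the gradable-1-year-image condition. Include in the repeated-measures model every eye without recorded graft failure that has any post-operative ECD (1 month or 1 year), and read the donor contrast at 1 year.
2. State that this main result applies to surviving grafts. This change recovers data from non-failed eyes; it does not address selection by failure.
3. Prespecify one supportive sensitivity analysis over all eyes in the primary analysis set: a rank-based comparison with failed grafts given the worst rank, clustered on participant. Say how non-failed eyes without a 1-year value are handled in it.

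The cost is some wording and one extra analysis, with no new data, visits or eyes. The downside is that the composite partly re-expresses the primary endpoint and is not in cells/mm². At 9% against 4%, failures alone could drive it, so it should be labelled supportive and not read as evidence on cell loss by itself.
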